#### **6.1.5. Sensitivity Analysis of the Primary Efficacy Endpoint**

Sensitivity and supportive analysis will be performed on the primary efficacy endpoint to quantify the possible impact of missing data, intercurrent events and to demonstrate the robustness of the conclusions. See below for details about missing data handling, placebo-based imputation, and a tipping-point analysis.

Furthermore, the primary analysis will be repeated using a hypothetical (de jure) estimand where data collected after rescue medication is initiated will be omitted. This can be viewed as addressing a per protocol estimand, or more simply the applicable estimand if all participants completed the first 3 weeks of follow-up without any rescue or without any missing data.

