#### **6.1.6. Missing Data**

Although the assumption of MAR, as used for the primary efficacy analysis method, is often reasonable in clinical studies, the possibility of MNAR data cannot be ruled out. Therefore, examining the robustness of the primary analysis results under MNAR is desired. Both a MNAR- and MAR-based analyses will be the basis upon which sensitivity of missing data is assessed.

Sensitivity analyses to deal with missing data and intercurrent events will be based on multiple imputation methods where missing values are imputed individually under different assumptions. Multiple imputation is a simulation-based approach where missing values are replaced using an appropriate stochastic model given the observed data and covariates, creating multiple completed data sets. These completed datasets are then analyzed using standard analysis methods (i.e., MMRM), and the different parameter estimates across the datasets are then combined to produce a unique point estimate and standard error taking into account the uncertainty of the imputation process. The following 2 sensitivity analysis models, one based on the standard MAR approach and the other based on the MNAR approach, will be used to examine robustness of the primary analysis results under the impact of missing data and intercurrent events.

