#### **6.1.7. Complete Multiple Imputation Differentiating Intereurrent Events**

For participants with complete data up to a particular visit, a distribution will be assumed for the assessments includes the outcome at that visit based on predefined missing categories and types of intercurrent events. The missing data then will be imputed based on specified algorithm which draws samples based on the prespecified distribution and algorithm. This process will be repeated a given number of times, resulting in the same number of complete analysis data sets. The MMRM analyses then will be performed separately for each of the completed analysis data sets, and the results will be combined into one multiple imputation inference ([Little and Yau 1996](#); [Schafer 1997](#)). Example SAS code is provided in [Appendix 3](#).

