### **Imputation distribution:**

The imputation distribution for the missing change from baseline in sBA at visit  $t$  will be assumed to follow a normal distribution. All randomized participants will be classified in one of the three categories based on the following rules: non-missing category, missing category 1, or missing category 2,

Non-missing category: Participants who have completed sBA assessment at baseline and Week 3 and have the change from baseline Week 3.

Missing category 1: Participants who discontinued treatment because of adverse events, lack of efficacy, noncompliance with study drug, death, physician decision, or required prohibited medication. These participants have missing change from baseline in sBA at visits including Week 3.

Missing category 2: Participants who discontinued treatment because of all other reasons other than the ones listed in category 1 and have missing the change from baseline in sBA at visits including Week 3, or participants who have completed 3 weeks treatment duration but are missing the change from baseline in sBA at visits including Week 3.

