### **Imputation algorithm:**

We use the following algorithm that relates the mean of the missing change from baseline in sBA at visit  $t$  to the missing categories defined above. The algorithm will be implemented independently within each treatment group:

- **Missing category 1**: randomly draw a sample from the normal distribution  $N(\mu_{25}, \sigma^2)$ , where  $\mu_{25}$  is the 25th percentile of the non-missing change from baseline in sBA at visit  $t$  and  $\sigma^2$  is the sample variance estimated using the non-missing change from baseline at visit  $t$ .
- **Missing category 2**: randomly draw a sample from the normal distribution  $N(\mu, \sigma^2)$ , where  $\mu$  is the mean of the non-missing change from baseline in sBA at visit  $t$  and  $\sigma^2$  is the sample variance estimated using the non-missing change from baseline at visit  $t$ .

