### 6.1.8. Tipping Point Analysis

An additional sensitivity analysis using the tipping-point approach will be conducted to assess the robustness of the primary analysis approach. If it is plausible that, for the active treatment group, the distribution of missing primary endpoint responses has a smaller expected reduction than that of the corresponding distribution of the observed primary endpoint responses, the conclusion under the MAR assumption should be examined. It is desired to impose a fixed and definite set of quantities to encapsulate the change in efficacy associated with withdrawal (missing) for the active treatment group, and independently for the placebo group. The tipping point multiple imputation analysis as described by Ratitch et al. (2013) will be applied. Tipping point analysis is a means of exploring the influence of missingness on the overall conclusion from statistical inference by positing a wide spectrum of specifications regarding the missingness mechanism (from less pessimistic to more pessimistic). The analysis finds a (tipping) point in this spectrum of specifications, at which conclusions change from being favorable to the experimental treatment to being neutral. The analysis will be based on the following procedure:

1. The missing data are filled in  $m$  ( $m = 10$ ) times to generate  $m$  complete data sets assuming that we do not differentiate missing data category (similar to assuming the algorithm for missing category 2).
2. The  $m$  complete data sets are analyzed by using standard procedures.
3. The results from the  $m$  complete data sets are combined for the inference.

4. Repeat the steps #1 to generate multiple imputed data sets, with a specified shift parameter that adjust the imputed values for observations in the relevant treatment group independently.
5. Repeat the step 2 for the imputed data sets with shift parameter applied.
6. Repeat the step 3 to obtain the p-value to see if the p-value is still  $\leq 0.05$ .
7. Repeat the steps 4-6 with more stringent shift parameter applied until the p-value  $> 0.05$ .

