#### **7.2.1. Summaries of Numeric Laboratory Results**

Descriptive statistics will be provided by indication for each laboratory test specified in the study protocol as follows:

- Baseline values
- Values at each postbaseline time point
- Change and percentage change from baseline at each postbaseline time point

A baseline laboratory value will be defined as the last measurement obtained on or prior to the date/time of first dose of study drug. Change from baseline to a postbaseline visit will be

defined as the visit value minus the baseline value. The mean, median, Q1, Q3, minimum, and maximum values will be displayed to the reported number of digits; SD values will be displayed to the reported number of digits plus 1.

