  /*--- Generates 10 imputed data sets ---*/

/*Step 1: Achieve Monotone Missing Data Pattern */

  PROC MI DATA=&DATA SEED=14823 NIMPUTE=10 OUT=MONO;
  ** Use numeric TRT01PN ;
  VAR BASE AVAL1 AVAL2 AVAL3; /*Refer to AVAL at Visits 5, 6, and 7*/
  MCMC IMPUTE=MONOTONE NBITER=5000 NITER =5000;
  BY TRT01PN;
  run;

/*Step 2: Impute all visits under MAR first, then apply delta adjustments
at each visit*/

  PROC MI DATA= OUTM1 SEED=14823 NIMPUTE=1 OUT=OUTM2;
  CLASS TRT01PN;
  BY _IMPUTATION_;
  VAR TRT01PN BASE AVAL1 AVAL2 AVAL3;
  MONOTONE REG (AVAL2 AVAL3);
  MNAR ADJUST( AVAL1 / SHIFT=&SJ ADJUSTOBS=(TRT01PN ='1') );
  MNAR ADJUST( AVAL2 / SHIFT=&SJ ADJUSTOBS=(TRT01PN ='1') );
  MNAR ADJUST( AVAL3 / SHIFT=&SJ ADJUSTOBS=(TRT01PN ='1') );
  RUN;
  PROC SORT DATA =OUTM1; BY _IMPUTATION_ TRT01PN USUBJID BASE; RUN;

/*Generate transpose of OUTM2 - skinny format before Step 3*/

/*Step 3: Run MMRM Analysis on Imputed Data */

PROC MIXED DATA=OUTM2 METHOD=REML;
  BY _IMPUTATION_;
  CLASS TRT01PN USUBJID AVISITN COUNTRY SEX;
  MODEL CHG = TRT01PN AVISITN COUNTRY SEX TRT01PN*AVISITN BASE /
  DDFM=KR;
  REPEATED / SUBJECT=USUBJID (TRT01PN) TYPE=UN;
  LSMEANS TRT01PN*AVISITN / CL DIFF PDIFF;
  ESTIMATE 'TRT S - P AT WEEK 24' TRT01PN -1 1
  TRT01PN*AVISITN 0 0 -1 0 0 1 / CL LOWER LOWERTAILED;
  ODS OUTPUT PARAMETERESTIMATES=PESTIMATES;
```

```
RUN;

/*First, sort the data of estimates by visit (variable "LABEL") */

PROC SORT DATA=PESTIMATES; BY LABEL; RUN:

/*Step 4: Combining estimates from each imputed data set */

PROC MIANALYZE DATA=PESTIMATES;
MODELEFFECTS ESTIMATE;
STDERR STDERR;
BY LABEL;
ODS OUTPUT PARAMETERESTIMATES=MIPARM;
RUN;
DATA MIPARM;
SET MIPARM;
SHIFT= &SJ;
RUN;

/*----- Output multiple imputation results -----*/

DATA &OUTPARMS;
SET &OUTPARMS MIPARM;
RUN;
%END;
%MEND MIPARMS;

/*Assume that the tipping point for the shift parameter that reverses the
study conclusion is between 0 and 100. The following statement performs
multiple imputation analysis for each of the shift parameters
0,10,20,30,...,100.*/

ODS LISTING CLOSE;
%MIPARMS (DATA=XXXX, SMIN=0, SMAX=100, SINC=10, OUTPARMS=PARMS1);

/* Step 5: Finding Tipping Point for Shift Parameter between 0 and 100
such that p-value is less than 0.05, below is an example for a tipping
point for the shift parameter between 40 and 50.
For a two-sided Type I error level of 0.05, the tipping point for the
shift parameter is greater than 40. The following statement performs

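### SAP 6.1.7 imputes participants who stopped for adverse events, lack of efficacy or death from the favourable tail of sBA change, and the code it points to is a different analysis

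*SAP*

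**What the plan says.** SAP 6.1.7 sorts participants with missing Week 3 sBA change into two categories. Category 1 is: "Participants who discontinued treatment because of adverse events, lack of efficacy, noncompliance with study drug, death, physician decision, or required prohibited medication". Category 2 is everyone else with missing data, including those who completed three weeks of treatment.

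The rule runs separately within each arm, with K = 5 imputations. Category 1 values come from a normal distribution whose centre "is the 25th percentile of the non-missing change from baseline in sBA at visit" t. Category 2 values are centred on the observed arm mean. Both use the observed variance.

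On direction, the primary objective is a reduction in sBA. Section 6.1 does not define the sign of change. SAP 7.2.1, on laboratory summaries, has change "defined as the visit value minus the baseline value", and SAP 7.3 uses the same order for weight and vital signs.

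On the structure of the sensitivity analyses, SAP 6.1.5 states: "See below for details about missing data handling, placebo-based imputation, and a tipping-point analysis". SAP 6.1.6 then announces: "The following 2 sensitivity analysis models, one based on the standard MAR approach and the other based on the MNAR approach". SAP 6.1.7 ends its opening paragraph with "Example SAS code is provided in" Appendix 3. The imputation code there consists of a placebo copy-reference program (10 imputations) and a tipping-point program.

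**The concern.** A sensitivity analysis for missing data should ask whether the result survives if those who left did worse than those who stayed. Category 1 holds the participants for whom that question matters most. On a visit-minus-baseline scale the 25th percentile is a larger fall in sBA than the arm mean, so the rule gives someone who stopped for lack of efficacy a better expected outcome than someone missing for a neutral reason.

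This runs against the SAP's own view of the pessimistic case. Section 6.1.8 says the missing-at-random conclusion should be examined if the missing-response distribution in the active arm "has a smaller expected reduction than that of the corresponding distribution of the observed primary endpoint responses". The macro call "MIPARMS (DATA=XXXX, SMIN=0, SMAX=100, SINC=10, OUTPARMS=PARMS1" then penalises the active arm with upward shifts in sBA. It also sits badly with protocol Section 10.4.1.1, which gives missing volixibat participants the placebo distribution and, for death, takes the worst case.

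At stake is whether this prespecified robustness check tests what it claims to test. The text and code add a second difficulty: a programmer following 6.1.7 and one following the code it cites would run different analyses.

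**Working it through.** **Inputs.** SAP 1.3: 100 per arm, difference 10, SD 25, two-sided alpha 0.05, 80% power. SAP 6.1.7: category 1 centred on the 25th percentile, category 2 on the mean, within arm. SAP 6.1.2: contrast is volixibat minus placebo, so benefit is negative. Neither document gives missingness rates; all rates below are assumptions.

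**The plan's own figure.** Power = Φ(10 / (25 × √(2/100)) − 1.96) = Φ(2.828 − 1.96) = 0.807 (0.804 by the noncentral t), which reproduces the stated 80%.

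**Distance between the two centres.** For a normal variable the 25th percentile is the mean minus 0.6745 × SD:

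- SD 20: 13.5 µmol/L
- SD 25: 16.9 µmol/L
- SD 30: 20.2 µmol/L

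For example, with true mean changes of −10 (volixibat) and 0 (placebo) at SD 25, category 1 is centred on −26.9 and −16.9. The 75th percentile would give +6.9 and +16.9.

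**Effect on the contrast.** Let pV and pP be the category 1 rates. With equal spread and shape in the two arms, shift = −16.86 × (pV − pP):

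| Volixibat / placebo (assumed) | Shift in contrast |
|---|---|
| 3% / 1% | 0.34 toward volixibat |
| 5% / 2% | 0.51 toward volixibat |
| 5% / 5% | 0 |
| 1% / 3% | 0.34 against volixibat |
| 5% / 10% | 0.84 against volixibat |
| 15% / 5% | 1.69 toward volixibat |

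**Unequal spread.** Each arm uses its own percentile, so equal rates cancel only if spread and shape match. At 5% in each arm with SDs of 30 (volixibat) and 20 (placebo), the shift is 0.05 × (20.23 − 13.49) = 0.34 toward volixibat. Reversing the SDs gives 0.34 against.

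**Simulation check.** This used Week 3 only, a t-test in place of the MMRM, K = 5 with Rubin's rules, and dropout unrelated to outcome. At 15% / 5% and a true difference of −10, the rule returned −11.57 (arithmetic: −11.69). With no true effect, that analysis rejected in volixibat's favour 6.4% of the time against a nominal 2.5%; at 10% / 10% the figure was 2.45%. These rates describe the sensitivity analysis only, and 15% / 5% is a large assumed imbalance.

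**Text against code.** The copy-reference program in Appendix 3 models missing values from the placebo arm. The tipping-point program adds a shift to imputed values. Neither contains missing categories, a percentile or a within-arm draw around one. Conversely, SAP 6.1.6 to 6.1.8 contain no placebo-based rule, although 6.1.5 promises one and protocol Section 10.4.1.1 describes one.

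**The case against.** **The sign is inferred.** Section 6.1 does not define it, and the two definitions sit in safety sections. The tipping-point code shifts the sBA value itself, so it shows that higher is worse, not how change is signed. Had change been baseline minus visit, the 25th percentile would be the unfavourable tail. This stands as a caveat, but I found nothing in the SAP that uses the opposite sign, and an undefined sign is itself a reason to amend 6.1.

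**The consequence is limited.** This is right. The primary MMRM does not use the rule. The tipping-point analysis does not separate missing categories and shifts in the pessimistic direction, so one correctly directed stress test remains. Missingness may be low: participants who stop drug stay on weekly visits (protocol Table 1 and Section 7.1), delivery samples taken before Week 3 are carried to the next window (SAP 3.8.3), and SAP 6.1.2 expects little missing data.

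**Text and code may be separate analyses.** On that reading, 5 imputations in 6.1.7 and 10 in the copy-reference code do not contradict each other. A reader might infer a conflict in the number of imputations, but that follows only if the two are meant as one analysis. What remains either way is a pointer to code that does not implement the section, and a promised analysis without SAP text.

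**Version lag and template code.** The SAP is based on protocol Version 1, so differences from the current protocol, including the handling of death, may be lag. The country, sex, Week 24 and one-sided terms are in code labelled as a sample, and the text already requires the primary model terms and two-sided tests. Lag does not explain 6.1.7 disagreeing with 6.1.8, or its pointer failing within the same document.

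**Conclusion.** The point holds, as a defect in one prespecified sensitivity analysis. On a visit-minus-baseline scale, SAP 6.1.7 centres the poor-outcome category about 0.67 SD (16.9 µmol/L at SD 25, under normality) on the favourable side of the neutral category. At assumed low rates the contrast moves by about 0.3 to 0.5 against a planned difference of 10; at 15% versus 5% it moves by 1.7.

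A reader might infer that the rule always flatters volixibat, or that it inflates the trial's type I error. The documents support neither. The rule applies in both arms, so an excess of such missingness on placebo moves the contrast against volixibat, and success is judged on the primary MMRM alone. The check is misdirected rather than uniformly lenient: it is easiest to pass when volixibat has the excess of poor-reason dropout, which is when it should be hardest.

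The missing SAP text for placebo-based imputation and the misdirected pointer hold whatever the sign and the missingness rates.

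**What to change.** Before unblinding:

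1. Define change from baseline in sBA in SAP 6.1 as visit minus baseline.
2. Move the category 1 centre to the unfavourable tail (the 75th percentile on that sign). Alternatively, drop the percentile rule and use placebo-based imputation as protocol Section 10.4.1.1 describes it: for all missing values in both arms, without reason categories. The protocol does not describe a hybrid that applies it to category 1 only.
3. Write the protocol's placebo-based analysis into the SAP text as the MNAR analysis, with its number of imputations, and tie the copy-reference code in Appendix 3 to it.
4. If 6.1.7 is kept, supply code that implements it, with the primary model terms and two-sided tests the SAP already requires.
5. Reconcile the handling of death in 6.1.7 with the composite, worst-case strategy in the protocol's primary estimand.

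The cost is SAP wording and minor reprogramming of one sensitivity analysis; placebo-based code already exists as a starting point. Design, conduct and sample size do not change. The downside for the sponsor is that the sensitivity result may be less favourable. Making the change after unblinding would turn the choice of tail, or of text over code, into a data-informed one.

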### **Analysis model:**

The complete MI method is described below:

- Impute missing values using the normal distribution specified in the above algorithm to impute values for all participants visit  $t$ . After imputation, all participants in the defined analysis population(s) will have non-missing change from baseline in sBA at visit  $t$ .
- Repeat the imputation for visits  $t+1, \dots, \text{Week 3}$ , until measurements at visits from visit  $t$  to Week 3 are imputed to form a complete dataset.

- Repeat the process  $K$  ( $K=5$ ) times, using the procedure described above to form  $K$  imputed complete datasets.
- Fit the MMRM model including terms for treatment, and all other terms as in the primary analysis model to each imputed dataset, to estimate the change from baseline during at Week 3 and its variance.
- Combine the results from the  $K$  imputed datasets using the SAS procedure MIANALYZE to derive the MI estimator.

We fit the analysis model (MMRM model specified before) to the  $k$ th imputed dataset, denoting the corresponding estimate of the variance  $V_k$ . The MI estimator,  $\tilde{\theta}_{MI}$ , is the average of the  $K$  individual estimators.

The estimated variance of  $\tilde{\theta}_{MI}$  is a combination of the between- and within-imputation variability as follows:  $V_{MI} = W + \left(1 + \frac{1}{K}\right)B$ , where  $W = \frac{1}{K} \sum_{k=1}^K V_k$  is the within-imputation variability and is  $B = \frac{1}{K-1} \sum_{k=1}^K (\tilde{\theta}_k - \tilde{\theta}_{MI})^2$  is the between-imputation variance. The statistic  $T = \frac{\tilde{\theta}_{MI} - \theta}{\sqrt{V_{MI}}}$  has an approximate  $t_V$  distribution

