## 15. APPENDIX 3 SAS SAMPLE CODES

A sample of the SAS code for sensitivity analysis using the copy-reference MI method is provided as below:

```
/*Generate transpose of adcf - wide format before Step 1*/
/*----- Generates 10 imputed data sets based on original (non-transformed)
data-----*/
/*Step 1: Achieve Monotone Missing Data Pattern */
PROC MI DATA=&DATA SEED=14823 NIMPUTE=10 OUT=MONO;
  /* Use numeric TRT01PN */
  VAR BASE AVAL1 AVAL2 AVAL3; /*Refer to AVAL at Visits 5, 6, and 7*/
  MCMC IMPUTE=MONOTONE NBITER=5000 NITER =5000;
  BY TRT01PN;
  run;

/*Step 2: Achieve Control-Based Copy-Reference Imputation */
PROC MI DATA=MONO SEED=14823 NIMPUTE=1 OUT=OUTM1;
  CLASS TRT01PN;
  By _IMPUTATION_;
  VAR TRT01PN BASE AVAL1 AVAL2 AVAL3;
  MONOTONE REG (AVAL2 AVAL3);
  MNAR MODEL (AVAL1 AVAL2 AVAL3/ MODELOBS = (TRT01PN = '0'));
  /*Control=Placebo*/
  RUN;
PROC SORT DATA =OUTM1; BY _IMPUTATION_ TRT01PN USUBJID LBASE; RUN;
/*Generate transpose of OUTM1 - skinny format before Step 3*/

/*Step 3: Run MMRM Analysis on Imputed Data */
PROC MIXED DATA=OUTM1 METHOD=REML;
  BY _IMPUTATION_;
  CLASS TRT01PN USUBJID AVISITN COUNTRY SEX;
  MODEL CHG = TRT01PN AVISITN COUNTRY SEX TRT01PN*AVISITN BASE / DDFM=KR;
  REPEATED / SUBJECT=USUBJID (TRT01PN) TYPE=UN;
  LSMEANS TRT01PN*AVISITN / CL DIFF PDIFF;
  ESTIMATE 'TRT S - P AT WEEK 24' TRT01PN -1 1
  TRT01PN*AVISITN 0 0 -1 0 0 1 / CL LOWER LOWERTAILED;
  ODS OUTPUT PARAMETERESTIMATES=PESTIMATES;
  RUN;

/*Step 4: Combining estimates from each imputed data set */
/*First, sort the data of estimates by visit (variable "LABEL") */
PROC MIANALYZE DATA=PESTIMATES;
  MODELEFFECTS ESTIMATE;
  STDERR STDERR;
  BY LABEL;
  ODS OUTPUT PARAMETERESTIMATES= MIPARM;
  RUN;
```

A sample of the SAS code for sensitivity analysis using the tipping-point approach is provided as below:

```
/*-----*/
```

```
/*--- Performs multiple imputation analysis ---*/
/*--- for specified shift parameters: ---*/
/*--- data= input data set ---*/
/*--- smin= min shift parameter ---*/
/*--- smax= max shift parameter ---*/
/*--- sinc= increment of the shift parameter ---*/
/*--- outparms= output parameters ---*/
/*-----*/
%MACRO MIPARMS( DATA=, SMIN=, SMAX=, SINC=, OUTPARMS=);
DATA &OUTPARMS;
  SET _NULL_;
RUN;
/*----- # of shift values -----*/
%LET NCASE= %SYSEVALF( (&SMAX-&SMIN)/&SINC, CEIL );
/*--- Multiple imputation analysis for each shift ---*/
%DO JC=0 %TO &NCASE;
  %LET SJ= %SYSEVALF( &SMIN + &JC * &SINC);

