multiple imputation analysis for shift parameters 40, 41, ..., 50*/

%MIPARMS (DATA=XXXX, SMIN=40, SMAX=50, SINC=1, OUTPARMS=PARM2);
/*The following statements display the p-values that are associated with
the shift parameters.*/
PROC PRINT LABEL DATA=PARM2;
VAR SHIFT PROBT;
TITLE 'P-VALUES FOR SHIFT PARAMETERS';
LABEL PROBT='PR > |T|';
FORMAT PROBT 8.4;
RUN;
```

A sample of the SAS code for van Elteren test is provided as below:

```
proc nparlway data=adef ;  
  strata BLGSTAGE BLITCHRO BLGDIAB;  
  class trt01p;  
  var chg;  
run;
```

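### The SAP's imputation numbers (5 in the 6.1.7 text, 10 in 6.1.8 and the sample code) and the unstated seed in 6.1.7 leave avoidable Monte Carlo error in the sensitivity analyses

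*SAP*

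**What the plan says.** Protocol 10.4.1.1 (Missing Data) leaves the details of the imputation to the SAP and says that both the number of imputations and the random-number seed will be fixed there before unblinding.

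The SAP then gives:

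- **6.1.7, analysis model.** K=5, directly before the words "times, using the procedure described above to form" the completed data sets. No seed is stated. For code, the section says "Example SAS code is provided in" Appendix 3.
- **6.1.8, tipping point.** m=10 "complete data sets assuming that we do not differentiate missing data category". A shift is added to the imputed values and made more severe until p exceeds 0.05. No step size is set.
- **Appendix 3.** Both multiple-imputation programs (copy-reference and tipping point) start with "PROC MI DATA=&DATA SEED=14823 NIMPUTE=10 OUT=MONO", that is, 10 imputations and seed 14823. Neither program carries out the category 1 and category 2 draws of 6.1.7.

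No reason is given for 5 or 10, and there is no limit on Monte Carlo error. SAP 6.1.2 expects little missing data at Week 3 but gives no rate.

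**The concern.** Multiple imputation gives a random answer. With few imputations, the pooled estimate and p-value depend noticeably on the seed, even though the trial data are fixed. These analyses are the SAP's evidence that the primary result survives missing Week 3 data (6.1.5 and 6.1.6). Two read-outs are exposed: whether p stays at or below 0.05, and the shift at which the result tips, which 6.1.8 passes on for clinical judgment.

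There are also two gaps in specification. A programmer who follows the 6.1.7 text runs 5 imputations, and one who follows the code it refers to runs 10. The category draws of 6.1.7 have no seed, so that analysis cannot be reproduced from the SAP, and the seed could still be chosen after the data are seen.

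**Working it through.** **Inputs.** From SAP 1.3: 100 per arm, difference 10, SD 25, two-sided alpha 0.05. From SAP 6.1.7: category 2 draws from a normal distribution with the arm's observed mean and variance at the visit, combined by Rubin's rules; K=5. From SAP 6.1.8: m=10. Assumptions: a missing fraction f of 5%, 10% or 20% per arm, an observed difference of 10 (design value) or 8, and a two-sample Week 3 comparison in place of the MMRM.

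**The plan's own figure.** SE = 25 × √(2/100) = 3.54. Power ≈ Φ(10/3.54 − 1.96) = Φ(0.87) = 80.7% (exact t: 80.4%). The stated 80% is reproduced.

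**Monte Carlo error of the estimate.** Each arm's mean contains f × 100 drawn values. The between-imputation variance of the difference is therefore f × SE², and the Monte Carlo SD of the pooled estimate is SE × √(f/K):

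- f=10%, K=5: 3.54 × √0.02 = 0.50 µmol/L
- f=20%, K=5: 3.54 × √0.04 = 0.71 µmol/L, which is 20% of the SE
- f=20%, K=10: 3.54 × √0.02 = 0.50 µmol/L
- f=20%, K=100: 3.54 × √0.002 = 0.16 µmol/L, which is 4.5% of the SE

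**p-values over seeds.** The data set was held fixed and only the seed varied (500 to 4,000 seeds). Central 95% range of p, and share of seeds with p>0.05:

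| Observed difference | Missing | K=5 | K=100 |
|---|---|---|---|
| 10 | 5% | 0.003-0.012; none | none |
| 10 | 10% | 0.003-0.02; essentially none | 0.006-0.009; none |
| 10 | 20% | 0.003-0.045; about 2% | 0.007-0.013; none |
| 8 | 5% | 0.016-0.047; about 1% | none |
| 8 | 10% | 0.015-0.07; about 14% | 0.026-0.036; none |
| 8 | 20% | 0.014-0.11; about 37% | 0.031-0.048; 1-2% |

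With 10 imputations, the number in the code, a difference of 8 gives p>0.05 for about 5% of seeds (10% missing) and 29% (20% missing).

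The difference of 8 is a borderline result in its own right. With 20% missing, the available-data SE is 25 × √(2/80) = 3.95, so 8/3.95 = 2.02 and p is about 0.043.

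**Tipping point.** A shift δ on the imputed active-arm values moves the estimate by f × δ. The Monte Carlo SD of the tipping point is therefore roughly SE × √(f/m)/f = SE/√(f × m). At a difference of 10, with the same draws at each shift and steps of 1:

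| Missing | m | Median | Formula, 1.96 × SD | Simulated central 95% |
|---|---|---|---|---|
| 10% | 10 | 26 | 1.96 × 3.54/√1 = ±6.9 | about 20-33 (lower limit 18 to 20 on repetition) |
| 10% | 100 | 26 | 1.96 × 3.54/√10 = ±2.2 | 24-28 |
| 20% | 10 | 12 | 1.96 × 3.54/√2 = ±4.9 | about 7-18 |
| 20% | 100 | 12 | 1.96 × 3.54/√20 = ±1.6 | 11-14 |

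Formula and simulation agree. With 10 imputations the range is about 11 to 13 µmol/L wide (18 − 7 and 33 − 20), slightly more than the difference of 10 for which the trial is powered.

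**The case against.** Several points on the other side stand.

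- **These are sensitivity analyses.** The primary MMRM in SAP 6.1.2 uses no imputation, so trial success and type I error do not depend on K or m.
- **Five applies to one place only.** A reader might infer that every missing-data analysis runs on 5. The documents do not support that: 6.1.8 and both Appendix 3 programs use 10.
- **The seed is fixed in the code.** SEED=14823 stands inside the tipping-point loop, so it is already the same for every shift and cannot be picked later. That gives repeatability but does not reduce the Monte Carlo error, and it does not cover the 6.1.7 category draws.
- **Missing data may be few.** Participants who stop drug continue weekly visits, and SAP 3.8.3 maps a delivery sample taken before Week 3 to the next window. On the other side, protocol 4.3.2.1 expects relatively few participants to stay on treatment beyond 3 weeks. The rate is unknown, hence the range shown.
- **Regression-based code is less noisy.** The Appendix 3 tipping program imputes from baseline and earlier visits, which lowers the between-imputation variance. With an assumed correlation of 0.7, a difference of 12, 20% missing and m=10, the tipping range is 19-26 µmol/L, against 15-26 with the marginal draws. The 6.1.8 text, however, describes something close to the category 2 rule, so both readings are open.
- **The step of 1 µmol/L is only illustrative.** One might read the SAP as committed to locating the tipping point to 1 µmol/L. The program is a sample: it steps by 10 first, and "multiple imputation analysis for shift parameters 40, 41, ..., 50" is presented as an example.

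**Conclusion.** The point holds as one of avoidable imprecision and incomplete specification in the sensitivity analyses. SAP 6.1.7 gives 5 imputations and no seed, the code it refers to runs 10, and neither number is justified.

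A reader might go further and infer that the same trial data could generally look robust or not robust depending on the seed. That does not follow. At the design difference of 10, with 10% or less missing, p varies but almost never crosses 0.05; with 20% missing and K=5, about 2% of seeds cross. The verdict becomes seed-dependent when the result is already near 0.05: at a difference of 8, about 14% of seeds with 10% missing and 37% with 20%.

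The tipping point is affected more generally. At m=10 it moves over about 11 to 13 µmol/L at the design difference, against about 3 to 4 µmol/L with 100 imputations.

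These sizes rest on an assumed missing rate, SD 25, marginal category 2 draws, and a two-sample comparison instead of the MMRM. They are approximate, and regression-based imputation would give somewhat narrower ranges. More imputations reduce only the Monte Carlo error; they do not test whether the imputation rules themselves are apt.

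**What to change.** Before unblinding, amend the SAP as follows:

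1. Use one prespecified number of imputations, for example 100, in 6.1.7, in 6.1.8 and in both Appendix 3 programs. At 20% missing this brings the Monte Carlo error to √(0.2/100) = 4.5% of the standard error. The figure of 100 is a working choice, not one taken from the documents.
2. State a seed for the 6.1.7 category draws, and add a program for them or correct the reference to Appendix 3.
3. Keep the existing fixed seed across shift values in the tipping-point search.
4. Report the Monte Carlo error of the pooled estimate beside each imputation result.

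The cost is a few edits to the text and code and minutes of computing. Nothing changes in trial conduct, data collection or the primary analysis.
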